#### 11.2.2.2 Reporting procedures

#### **Procedures for reporting Adverse Events**

The collection of AEs is from the time that subjects signs the ICF to their final visit.

At each post enrolment visit, the Investigator (or sub-Investigator) will question the subject about AEs using an open non-persuasive question to elicit reporting of AEs, for example "Have you noticed any change in your health since the last visit?" Directed questioning and examination will then be performed as appropriate.

Any AE occurring during the AE reporting period, whether it is related to the trial drug(s) or not, will be recorded immediately in the source document, and described on the Adverse Event Form of the [CRF along with the date of onset, severity, relationship to the trial drug(s), and outcome, without omitting any requested and known information. Additional information may be requested under certain circumstances. Adverse Events (AEs) assessed as related to the treatment will be monitored until they are completely or satisfactorily resolved. Other AEs will be monitored until the last visit if they are not resolved or satisfactorily resolved.

The Investigator will obtain and maintain in the subject's files all pertinent medical records, information and medical judgment from colleagues who assisted in the treatment and follow up of the subject. If necessary, the Investigator will contact the subject's personal physician or hospital staff to obtain further details.

#### Procedure for reporting a Serious Adverse Event

For an SAE occurring during the period of the clinical trial, regardless of whether it is related to the treatment or not, and of whether it is expected or not, the Investigator must do the following:

- Take prompt and appropriate medical action, if necessary. The safety of the subject is the first priority.
- Immediately inform the Clinical Safety Responsible (from the UBC Company) designated by Drug Delivery Solutions Aps (DDS) c/o MC2 Therapeutics A/S of the event by email or Fax and discuss further actions to be taken.

#### Email: [contact]

#### [contact]

Additional contact details are provided in the Investigator's site file.

- Complete the Adverse Event Form provided in the e*CRF* as fully as possible.
- Ensure that the event is classified as an SAE.
- Complete the standard Serious Adverse Event Form. Fax or scan and send by e-mail the completed form accompanied by demographics, medical history, previous and concomitant

Clinical Trial Protocol MC2-01-C4

Final Approved Version 20/08/2018

therapies and adverse event pages of the CRF, and any other relevant information or medical records (e.g., laboratory test results) within 24 hours to UBC.

- Monitor and record the progress of the event until it resolves or reaches a clinically stable outcome, with or without sequelae. For all additional follow-up evaluations, first inform the CSR of the outcome by telephone, then fax or scan and send by e-mail all additional follow-up information to the UBC within 24 hours. Serious Adverse Events (SAEs) will be monitored until the Investigator and Sponsor agree that the event is satisfactorily resolved.
- Obtain and maintain in his/her files all pertinent medical records, information, and medical judgments from colleagues who assisted in the treatment and follow-up of the subject. If necessary, contact the subject's personal physician or hospital staff to obtain further details.
- Inform the CSR of the final outcome of the event. Send a revised or updated Serious Adverse Event Form and Adverse Event Form, if appropriate.
- Comply with the applicable regulatory requirement(s) related to the reporting of SAEs to the Institutional Review Board (IRB) / Independent Ethics Committee (IEC).

### **Responsibilities of the Sponsor:**

### For Suspected Unexpected Serious Adverse Events (SUSAR):

For the researches mentioned in n°1 of the article L. 1121-1 of the Public Health Book concerning drugs and cells therapies, the Sponsor has to declare to the competent authority any suspicion of unexpected Serious Adverse Events (SUSAR) occurring in France and outside the national territory within the following deadlines:

1. In the case of suspected unexpected Serious Adverse Events having caused death or having endangered life, without delay starting from when the Sponsor has been informed;

2. In the case of the others unexpected Serious Adverse Events, at the latest within fifteen days starting from when the Sponsor has been informed.

The Sponsor declares in the form of a follow-up report to the ANSM the relevant further information concerning the unexpected Serious Adverse Events. In the case of suspicion of unexpected Serious Adverse Events having caused death or having endangered life, these further information are notified within eight days starting from the declaration mentioned in 1 °. In the other cases of suspicion of unexpected Serious Adverse Events and in case of new fact mentioned in the article L. 1123-10, the relevant further information are transmitted within a new deadline of eight days starting from the declaration mentioned in 2 °.

> Each SUSAR must be reported in an individual email message and should be sent to: [contact]. A declaration should be also sent to the Eudravigilance: (clinical trials module) https://eudravigilance.ema.europa.eu.

The subject line should be written as follows: SUSAR\_yyyymmdd\_name of substance (or trial code no.)\_Worldwide unique case identification number\_CT,

Ex: SUSAR\_20140115\_SUBSTANCE\_123456789\_CT.

CONFIDENTIAL

Clinical Trial Protocol MC2-01-C4

Final Approved Version 20/08/2018

Particular case: SUSARs regarding a clinical trial on medicinal products involving healthy volunteers (whatever the clinical trial phase): the subject line should be written as follows: *EC-VS-SUSAR\_yyyymmdd\_name of substance (or trial code no.)\_Worldwide unique case identification number\_CT.* 

The following document should be attached to the message: - CIOMS form (PDF format) / File name labelled as follows: yyyymmdd\_name of substance (or trial code no.)\_Worldwide unique case identification number\_CT\_C.

Ex: 20140115\_SUBSTANCE\_123456789\_CT\_C.

An acknowledgement of receipt will be automatically sent by return email.

For Expected serious adverse reaction or other serious adverse event (clinical trials on a medicinal product involving healthy volunteers):

The Sponsor has to declare without delay to the competent authority the expected Serious Adverse Events and all other Serious Adverse Events occurring in France and outside the national territory.

> Each notification must be reported in an individual email message and should be sent to: [contact]

The subject line should be written as follows: **EC-VS-EIGA** yyyymmdd\_name of substance (or trial code no.)\_Worldwide unique case identification number\_CT.

The following document should be attached to the message: - CIOMS form (PDF format) / File name labelled as follows: yyyymmdd\_name of substance (or trial code no.)\_Worldwide unique case identification number\_CT\_C.

An acknowledgement of receipt will be automatically sent by return email.

*For other serious adverse event which occurred in France:* The only difference compared to other SAEs is that the subject line should be written as follows: *EC-VS-EVIG yyyymmdd\_name of substance (or trial code no.)\_Worldwide unique case identification number\_CT.* 

## 11.2.3 Pregnancy

Any pregnancy occurring from the date of the informed consent signature and until trial completion must be reported immediately of UBC as soon as it becomes known to the investigator and no longer than 24 hours after first knowledge of the occurrence of the pregnancy (11.2.2.2).

## 11.3 Other assessments

NA

#### 11.4 Appropriateness of measurements

Visual assessment of the skin blanching used for US ranking trial (13).

Clinical Trial Protocol MC2-01-C4

Safety is documented by the recording of adverse events, the global cutaneous tolerance, the physical examination and the vital signs assessments.

## **12 CLINICAL TRIAL VISITS DESCRIPTIONS AND PROCEDURES**

## **12.1** Description of Clinical Trial Visits

A written, signed Informed Consent Form (ICF) must be obtained prior to performing any trial related evaluations and/or procedures for this protocol. The Investigator representative will review and explain the nature of the trial to the Subject and particularly the prohibited activities and the constraints of the trial. A copy of the signed and dated ICF will be provided to the Subject, another copy will be filed in the Investigator site file.

Visual assessments must be conducted by two trained readers for skin blanching response.

Schedule of Assessments is described in Table 1.

### 12.1.1 Screening Phase

The Screening period takes place within 15 days to 1 day prior to Day 1 visit.

The Investigator or the designed trial person will:

- Review and explain the nature of the trial in detail to the Subject, particularly the prohibited activities and the constraints of the trial.
- Insure that the Subject read and sign the Informed Consent Form. Give a copy to the Subject.
- Perform a urinary pregnancy test for female subject of childbearing potential.
- Assign to the Subject a Subject identification number and give his/her a Subject card.
- Collect information regarding demographics, relevant medical history, previous medications/procedures use and concomitant therapies/procedures use.
- Check inclusion/exclusion criteria.
- Perform a physical examination of the Subject, check vital signs (blood pressure, pulse rate).
- Test for assessment of the blanching response with the reference product on healthy skin
- Complete the Subject Screening & Enrolment log.
- Give the Subject an appointment for the Day 1 visit.

Clinical Trial Protocol MC2-01-C4

12.1.2 Test Phase

#### 12.1.2.1 Baseline visit (Day 1)

The Investigator or the designated trial person will:

• Re-check inclusion/exclusion criteria including concomitant therapies.

• Ask the Subject about AEs by asking an open-ended question taking care not to influence the Subject's answer, such as "Have you noticed any change in your health since the last visit?" Record all events, as appropriate on the corresponding CRF pages.

• Ask the Subject whether there have been any changes to his/her concomitant therapies/procedures (added, removed, or changed) since the previous visit. Document all changes on the Concomitant Therapy form of the CRF.

• Perform a urinary pregnancy test for female subject of childbearing potential. The test must be negative to continue the trial.

• Preselect seven test sites, 2.2 cm in diameter on the anterior surface of the forearms (4 sites on one forearm and 3 on the other). Mark the selected sites with a cutaneous marker.

- Number the selected test sites from 1 to 7 (Z1-Z7).
- Assign a randomization number to the Subject (this number will be assigned to enrolled Subjects in a sequential order and no numbers will be omitted).
- Complete the Subject Screening and enrolment log and the Subject Identification Code List form indicating the last name, first name and date of inclusion.
- A member of staff other than the Investigator will:
- Apply 20µL of the tested products on the Subject's selected areas using gloves and a multipipette Eppendorf.
- Protect the test sites with a non-occlusive gaze dressing (for 16 hours).
- Instruct the Subject to avoid wetting areas (showers, swimming, bath, sauna, Hamman are not allowed).
- Schedule an appointment for the next Visit.

#### 12.1.2.2 Day 2

At this visit, the Investigator or the designated trial person will:

 Ask the Subject about AEs by asking an open-ended question taking care not to influence the Subject's answer, such as "Have you noticed any change in your health since the last visit?" Record all events, as appropriate on the corresponding CRF pages.

Clinical Trial Protocol MC2-01-C4

Final Approved Version 20/08/2018

 Ask the Subject whether there have been any changes to his/her concomitant therapies/procedures (added, removed, or changed) since the previous visit. Document all changes on the Concomitant Therapy form of the CRF.

A member of staff other than the Investigator/trained readers will:

Remove the dressings and the product excess on each test site.

Two distinct trained readers will:

- Assess the skin blanching response (2 trained readers) on each test site 2 hours after removal of the products,
- Assess local tolerance by test site using a 4 point-scale for each site.

### 12.1.3 Follow-up Phase

If an adverse event (serious or non-serious), classified as possible or probably related to the trial medication or not assessable in relation to the trial medication, is ongoing at the subject's last visit, a follow-up visit/contact will take place 14 ( $\pm$ 2) days after that visit.

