#### At Day 1:

Will be performed:

- Re-check of inclusion/exclusion criteria
- Urine pregnancy test for female subjects of child-bearing potential
- Selection of seven tests sites
- Application of the products under non-occluded conditions for 16 hours.

	
 
At Day 2:
 
Removal of the products
 
Visual assessments of the skin blanching by 2 trained observers 2 hours after the removal.
 
Assessment of the local tolerability.
 

	During the treatment phase local and systemic adverse events will be reported on an ongoing basis.
	Follow-up:
	If an adverse event (serious or non-serious), classified as reasonable_possible related to the trial medication is ongoing at the subject's last visit, a follow-up visit/contact will take place 14 (±2) days after that visit.
Total number of subjects (Planned):	60 subjects will be screened in order to have 36 subjects randomized and at least 30 subjects completed.
Number of clinical trial centers (Planned):	Single center
Region / country involved (Planned):	France
Clinical trial duration:	2 months
Duration of subject participation:	

Two days (plus the screening period and the follow-up phase).

CONFIDENTIAL

Inclusion criteria:	
 
Male or female subjects, aged 18 years to 50 years old, having signed and dated an informed consent,
 

	2. Non-smoker subjects,
	
 
Subjects demonstrating adequate vasoconstriction to Betamethasone Dipropionate (Augmented) cream within 15 day prior to dosing (unoccluded application of Betamethason Dipropionate (Augmented) cream for 4-6 hours must show a visua score of skin blanching of at least one unit (visual scale (0-4)),
 

	
 
Subjects without any signs of skin irritation/disease/disorders/symptoms or blemishes on test sites (e.g erythema, dryness, roughness, scaling, scars, moles, sunburn),
 

	
 
Female subject of non-child bearing potential, defined as surgicall sterile or post-menopausal (at least one year post cessation o menses),
 

	6. Female of childbearing potential who has been, in the opinion of the Investigator, using an approved method of birth control (e.g. ora contraception pill or patch, intra-uterine devices, contraceptive implants or vaginal rings, condoms, bilateral tubal ligation) at tria entry and agree to continue until the end of last trial visit.

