## 7.1.3 Follow-up Phase

A follow-up visit/contact (telephone contact or visit according to the investigator's discretion) will take place up to 14 ( $\pm$ 2) days after Day 2 if any of the below conditions apply when the subject has completed the trial:

- The subject has a local tolerability score >0,

Clinical Trial Protocol MC2-01-C4

Final Approved Version 20/08/2018

- The subject has an ongoing non-serious adverse event classified as reasonably possibly related to the investigational products,

- The subject has an ongoing SAE.

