# 9.3 Withdrawal Criteria

Subjects may withdraw for any of the following reasons:

- 1. Unacceptable treatment efficacy: the investigator is free to withdraw the subject at any time for medical reasons.
- 2. Unacceptable adverse events: any adverse event that the investigator or the subject considers unacceptable.
- 3. Exclusion criteria: any exclusion criteria which emerge/become apparent during the subject's participation in the clinical trial.
- 4. Voluntary withdrawal: subjects will be free to withdraw from the clinical trial at any time and for any reason.
- 5. Other reasons: other reasons than stated above which requires the subject to (be) withdraw(n) should be specified.

Subjects who are discovered, after enrolment/randomization, not to have fulfilled all in/exclusion criteria at time of enrolment, should be withdrawn from treatment unless the investigator, based on clinical and ethical evaluation, finds withdrawal inappropriate. Such deviation(s) from the Clinical Trial Protocol must be reported to (and IEC/IRB, as appropriate) and recorded in the Clinical Trial Report.

The assessments at the early withdrawal visit should be attempted to be completed for all subjects who withdraw from the treatment for any reasons. The ultrasound measurement should be performed at this early withdrawal visit.

In case of early withdrawal from the trial, a follow-up visit/contact should be planned 14 (+/- 2) days after the last visit for those subjects having an adverse event classified as reasonably possibly related to the trial medication, unless final outcome of the event has been determined in the meantime.

Reason(s) for withdrawal will be recorded in the CRF. Subjects withdrawn will not be substituted.

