## 11.1.2 Assessment of Local Tolerability

At Day 2, the (sub)investigator will assess each test site for local tolerability according to the scale in Table 4.

Table 4 - Local tolerability scale

Score*	Description
0	No reaction
0.5	Only slight erythema
1	Only erythema
2	Erythema with papules or oedema
3	Erythema, oedema with papules, oedema with vesicle
4	Blisters
IR	Irritant reaction including: miliaria (sweet rash), follicular pustules, burn-like reactions, dry scales

Subjects with a local tolerability score >0 will be re-assessed at a follow-up visit.

Cutaneous reactions scored as local tolerability will be reported as local AEs.

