## Relationship to the trial drug(s)

The Investigator is to determine whether there is a reasonable causal relationship between the trial drug(s) and the AE. Medical judgment should be used to determine the relationship, considering all relevant factors including the pattern of reaction, temporal relationships, positive challenge or rechallenge, relevant medical history, and confounding factors such as co medication or concurrent diseases.

The expression "reasonable causal relationship" is meant to convey in general that there are facts or arguments to suggest a causal relationship (ICH E2A, Section IIIA 1).

The relationship assessment for an AE is to be completed using the following definitions as a guideline for all AEs occurring during clinical trials:

• Reasonable Possibility:

According to the reporting Investigator, there is a reasonable possibility (i.e., suggestive evidence or arguments) that there is a causal relationship irrespective of the dose administered between:

The trial drug (investigational product, active reference, or vehicle, etc.) and the AE,

The clinical trial protocol procedure (e.g. product application, etc.) and the AE.

• No Reasonable Possibility:

This document will be regarded as confidential and proprietary in nature and will not be disclosed to any third party without sponsors written consent

Page 39/54

Clinical Trial Protocol MC2-01-C4

Final Approved Version 20/08/2018

No suggestive evidence or arguments can be identified regarding a causal relationship between the trial drug or the clinical trial protocol procedure and the AE.

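### The follow-up trigger in protocol 12.1.3 uses causality ratings the trial does not record and is narrower than the three-trigger rule in 7.1.3 and the SAP, so the passages need reconciling

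*Protocol*

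**What the plan says.** **The rule in the visit descriptions.** Protocol 12.1.3 arranges a visit or contact when an adverse event, serious or not, is ongoing at the last visit and is "classified as possible or probably related to the trial medication or not assessable in relation to the trial medication". Tolerability scores are not mentioned.

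**The causality scale.** Protocol 11.2.2.1 has two levels. The first applies where "According to the reporting Investigator, there is a reasonable possibility (i.e., suggestive evidence or arguments) that there is a causal relationship", either with the trial drug or with a protocol procedure. The second is "No Reasonable Possibility". There is no third level.

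**The three-trigger rule.** Protocol 7.1.3 calls for follow-up if any one of three conditions holds: "The subject has a local tolerability score >0"; an ongoing non-serious event rated as related; or "The subject has an ongoing SAE". The first and third carry no causality condition. Protocol 7.1, Table 1 footnote 2, and SAP 3.1 and 3.3 give the same three.

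**Two further versions.** The synopsis requires that the event be one "classified as reasonable_possible related to the trial medication is ongoing". Section 9.3, for early withdrawals, plans follow-up "for those subjects having an adverse event classified as reasonably possibly related to the trial medication". Neither has the score trigger or a causality-free SAE trigger.

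**Separate duties.** Protocol 11.1.2 says: "Subjects with a local tolerability score >0 will be re-assessed at a follow-up visit". SAP 4.2 repeats this, and both make every scored skin reaction a local adverse event. Protocol 11.2.2.2 has related events monitored to resolution, all SAEs monitored until the investigator and sponsor agree they are resolved, and other events monitored only to the last visit.

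**The concern.** The trigger decides which subjects have any record after Day 2. Section 12 is where site staff look up what to do at each visit, and its follow-up rule is both worded in undefined ratings and narrower than the rule elsewhere.

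Three outputs depend on that record:

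- Local tolerability is the only secondary objective. Both schedules plan a follow-up tolerance assessment, and protocol 13.3.1 summarises the score by visit.
- Protocol 13.3.2 and SAP 5.3.2 take causality from the last report of an event, so a follow-up report can change whether it counts as an adverse drug reaction.
- The same sections take intensity as the worst ever recorded, so a follow-up report can also change the reported intensity.

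If a site works from 12.1.3 alone, the Day 2 causality rating helps decide which reactions receive a later report. For a non-serious event rated unrelated, the last visit is then Day 2, and monitoring under 11.2.2.2 may end there.

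**Working it through.** This is a comparison of wording. The plan gives no figure on this point to reproduce.

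**Step 1: labels.** Section 12.1.3 uses *possible*, *probably related* and *not assessable*. Section 11.2.2.1 offers *Reasonable Possibility* and *No Reasonable Possibility*. None of the three labels in 12.1.3 is a recordable rating. Two readings follow:

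- Natural: *possible* or *probably related* means *Reasonable Possibility* (RP).
- Literal: no event can carry the label, so nothing triggers.

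**Step 2: apply each rule.** Take a subject with an ongoing event at Day 2. There are 2 (serious or not) × 2 (RP, or NRP for the other level) × 2 (score above 0, or 0) = 8 profiles. For simplicity, one rating covers the event and any scored reaction, and RP here means related to the medication.

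| Event | Rating | Score | 7.1.3 | 12.1.3 natural | 12.1.3 literal |
|---|---|---|---|---|---|
| SAE | RP | >0 | yes | yes | no |
| SAE | RP | 0 | yes | yes | no |
| SAE | NRP | >0 | yes | **no** | no |
| SAE | NRP | 0 | yes | **no** | no |
| Non-serious | RP | >0 | yes | yes | no |
| Non-serious | RP | 0 | yes | yes | no |
| Non-serious | NRP | >0 | yes | **no** | no |
| Non-serious | NRP | 0 | no | no | no |

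Section 7.1.3 triggers in 7 of 8. On the natural reading 12.1.3 triggers in 4 of those and misses 7 − 4 = 3. On the literal reading it misses 7 − 0 = 7. The synopsis trigger gives the same 4 of 7. Section 9.3 has the same gaps but governs early withdrawals, whereas 7.1.3 applies to subjects who have completed, so 9.3 is not scored in this table.

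**Step 3: a gap the table does not show.** Section 11.2.2.1 counts procedure-related events as *Reasonable Possibility*, but 12.1.3 speaks only of trial medication. A reaction attributed to the protective ring or dressing could be rated RP and still fall outside 12.1.3.

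**Step 4: what other sections recover.** All three missed profiles are covered elsewhere. Section 11.1.2 and SAP 4.2 require re-assessment for any score above 0, and 11.2.2.2 requires every SAE to be monitored.

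**Step 5: visit or contact.** Section 11.1.2 and SAP 4.2 require a visit for a score above 0. Section 7.1.3, Table 1 footnote 2 and SAP 3.3 allow a telephone contact, which may yield no re-scored site.

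**Step 6: size.** Tolerability is scored at 7 sites in 36 planned subjects, 7 × 36 = 252 sites. The documents give no expected rate of scores above 0 or of unrelated SAEs, so the number of affected subjects cannot be derived.

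**The case against.** The strongest reply is that the rest of the plan already protects the data. Section 11.1.2 and SAP 4.2 re-assess any score above 0 regardless of causality, and 11.2.2.2 monitors every SAE. Section 12.1 points to Table 1, whose footnote lists all three triggers, and 12.1.3 never says its trigger is the only one. A related, ongoing reaction still triggers 12.1.3, because every scored reaction is an adverse event. SAP 5.3.1 summarises tolerability by product and worst score, without the by-visit split, and no analysis of resolution is planned. All of this is correct and limits the effect.

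A reader might go further and infer that 12.1.3 triggers for nobody, because its labels cannot be recorded. The documents do not support that as the working reading. The related-event wording in 7.1.3, 9.3, the synopsis and the SAP does not match the 11.2.2.1 labels exactly either, so the same literalism would defeat the related-event trigger there too. An investigator would take *possible or probably related* to mean *Reasonable Possibility*.

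A reader might also infer that SAEs are left out of 12.1.3, or that nothing else covers an unrelated skin reaction. Neither holds: related SAEs remain in 12.1.3, and 11.1.2 covers the reaction.

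The contradiction itself stands. Sections 11.1.2 and 7.1.3 do not repair 12.1.3. They require follow-up where 12.1.3 does not, and the protocol does not say which prevails.

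**Conclusion.** The inconsistency is real and should be corrected. Section 12.1.3 relies on ratings outside the trial's scale, lacks the score trigger and narrows the SAE trigger to related events. The synopsis and 9.3 share the last two gaps.

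On the natural reading, a site using 12.1.3 alone would miss scored reactions not attributed to the medication (unrelated or procedure-attributed) and SAEs judged unrelated. That is 3 of the 7 profiles that 7.1.3 would follow, plus the procedure-attributed case. The profile count is unweighted, depends on how profiles are divided, and says nothing about how many subjects are involved.

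The consequence is uneven follow-up tolerability and adverse-event outcome data, depending on which section a site follows. It is not blanket loss, because other sections cover the missed cases when applied. The Day 2 tolerability scores and the primary blanching analysis are unaffected. The conclusion assumes that staff may act on 12.1.3, the synopsis or 9.3 without cross-checking 7.1.3, 11.1.2 and Table 1.

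**What to change.** Reconcile the follow-up wording in the protocol (synopsis, Table 1 footnote 2, 7.1, 7.1.3, 9.3, 11.1.2 and 12.1.3) and the SAP (3.1, 3.3 and 4.2) to a single trigger list. Which triggers belong in it is for the sponsor to decide. The list should:

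- use only the two causality categories of 11.2.2.1, and say whether procedure-attributed events count;
- state whether a score above 0 requires a visit or may be handled by telephone;
- state whether it also applies to early withdrawals.

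Then have 12.1.3, the synopsis and 9.3 refer to that list instead of restating it.

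The cost is protocol and SAP wording, and possibly a few follow-up contacts that other sections already plan. It needs no new procedure, extra subjects or change to the primary analysis.
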